3.2. Prospective study

The prospective stage will take place in a clinical environment, where HCPs will use the 2D-BioPAD diagnostic aid to measure AD blood biomarkers in individuals referred to the three study centres for assessment of suspected AD/dementia disease.

In *Step 1*, a small-scale feasibility test run will be performed in the three clinics. The main objective is to refine the appropriate procedure for using the diagnostic aid by identifying constraints (e.g., at which time of the day the measurement should take place), limitations (e.g., how easy it is to use), and potential improvements.

In *Step 2*, the clinical evaluation and validation will be conducted in (i) up to 300 individuals with subjective cognitive complaints, MCI, or dementia referred to the three clinical study centres for assessment, and (ii) the HCPs using the 2D-BioPAD diagnostic aid. Up to one year follow-up will be included for patients with inconclusive diagnosis following the initial assessment. The primary objectives are to (i) evaluate and validate the performance of the 2D-BioPAD diagnostic aid under real-world clinical conditions and use cases, and (ii) evaluate feedback from HCPs and patients including e.g. acceptability, trust, satisfaction, usability, and experience of using the 2D-BioPAD diagnostic aid compared with study centre-specific standard procedures for acquiring blood measurements in clinical practice. Performance of the 2D-BioPAD diagnostic aid will be compared with the same benchmarking equipment for plasma biomarkers (measured for all prospective study samples) and state-of-the-art equipment for CSF biomarkers (measurements as available from routine assessments conducted at the clinical study centres) as described above for the retrospective study.

4. Implementation and evaluation

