4.3.3. Recruitment

All clinical study centres have well-established recruitment procedures for research studies, including both HCPs and patients. Recruitment timeline for the 2D-BioPAD clinical pilot study is shown in section 4.5. Continuous recruitment will be conducted until a total sample of ≈ 300 patients will be reached. Step 1 (feasibility test-run) will include the first 30 recruited patients (10 per study centre). In Step 2, recruitment will be scaled up to include 270 patients until the total $N \approx 300$ is reached.

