4.4.3. Data analysis

Analyses will include e.g.:

- Correlations (Spearman/Pearson as appropriate) between 2D-BioPAD markers and benchmarking plasma markers. Statistical tests for comparing correlation coefficients will be used where applicable.
- Linear regressions and plots of 2D-BioPAD markers and benchmarking plasma markers.
- Bland-Altman comparison of 2D-BioPAD markers against benchmarking plasma markers.

Between-group comparisons of 2D-BioPAD AD plasma biomarker levels will be conducted using e.g., Mann-Whitney U test, t-test, or ANOVA as appropriate. Groups will be defined according to both clinical and biomarker-based characteristics. Diagnostic groups will be based on diagnosis established following centre-specific standard assessments, e.g., AD dementia, other dementia, MCI, or control. Biomarker-based groups will be defined using:

- For all participants, AD blood biomarkers measured with benchmarking equipment. Cut-offs will be based on existing literature (where available) and/or data-driven, e.g., using Gaussian mixture modelling.
- For participants with available AD CSF biomarkers from standard assessments, grouping will be based on established cut-offs.
- Exploratory analyses will consider ATN-based categorizations using state-of-the-art CSF and/or benchmarking plasma biomarkers.

To assess the potential impact of other parameters, e.g., demographics, comorbidities, liver and/or kidney function, APOE genotype (where available), such parameters will be added as covariates in the analyses.

Discrimination accuracies of 2D-BioPAD AD plasma biomarkers will be determined with logistic regression models and receiver operating characteristic curve (ROC) analysis. When predicting diagnosis or CSF-based biomarker +/- status, for each AD blood biomarker the area under the receiver operating characteristic curve (AUC) of the ROCs for 2D-BioPAD and benchmarking measures will be compared with DeLong test. Sensitivity, specificity, positive and negative predictive values will be assessed for different 2D-BioPAD biomarker cut-offs. Initial analyses will consider each AD plasma biomarker individually. Further analysis will investigate combinations of plasma biomarkers to determine which combinations have the best discrimination accuracy.

AD plasma biomarkers (2D-BioPAD versus benchmarking equipment) will be investigated in relation to cognitive, clinical, and other data using appropriate regression models.

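### Device cut-offs and marker combinations are explored in the same patients who supply the reported accuracy, with no locked cut-off or internal validation, so a best figure reported from that search would be optimistic

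*Protocol*

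**What the plan says.** Table 9 of the Protocol makes sensitivity, specificity and the two predictive values, device versus benchmark and against clinical AD diagnosis, the first primary prospective outcome. Table 8 makes the same measures, for the prototype, primary in the 60 retrospective samples. Section 4.4.3 states noninferior accuracy as the main hypothesis.

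All four measures need a cut-off. The only statement on how they will be obtained is in section 4.4.3: "Sensitivity, specificity, positive and negative predictive values will be assessed for different 2D-BioPAD biomarker cut-offs". On combining markers, the same section adds: "Further analysis will investigate combinations of plasma biomarkers to determine which combinations have the best discrimination accuracy". It also gives a comparison that needs no cut-off, for each single marker: "AUC) of the ROCs for 2D-BioPAD and benchmarking measures will be compared with DeLong test".

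Cut-offs for the benchmark are mentioned once, in a list that opens "Biomarker-based groups will be defined using" and continues: "Cut-offs will be based on existing literature (where available) and/or data-driven, e.g., using Gaussian mixture modelling".

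On the validation set, section 3.2 says of Step 2 that "the clinical evaluation and validation will be conducted in (i) up to 300 individuals with subjective cognitive complaints, MCI, or dementia". Section 4.3.3 says "In Step 2, recruitment will be scaled up to include 270 patients", the first 30 patients being Step 1.

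**The concern.** When a cut-off or a marker combination is picked because it does best in a dataset, its performance in that dataset overstates what it would do in new patients. The Protocol describes exactly such an exploration, names only the device when it speaks of several cut-offs, and gives no step that separates choosing from scoring. The results are meant to validate the device and to plan confirmatory studies, so an inflated sensitivity or specificity would be carried into the design of the next study.

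Two smaller matters go with this. First, the documents do not say which cut-off rule the benchmark follows in the primary comparison, so it is open whether the two platforms are treated alike. Second, section 3.2 places Step 2 in up to 300 patients, while section 4.3.3 gives Step 2 as 270. The first 30 are patients in whom the procedure of use is still being refined.

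**Working it through.** **1. The plan's own figure.** 30 (Step 1) + 270 (Step 2) = 300, and 3 centres × 100 = 300. Both agree with section 4.3.3.2 and Table 7. Table 7 justifies 300 by precedent only, so there is no power calculation to reproduce.

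**2. Inputs.** From the Protocol: N=300 prospective, 60 retrospective samples, CSF results in about 100 to 150 of the 300, and up to five markers on the device. The Protocol gives no expected accuracy, prevalence, correlation between platforms or margin. The following are therefore assumptions:
- Single marker: binormal; equal true AUC on both platforms (0.80 or 0.90); within-class correlation 0.8; AD prevalence 50%; 1,500 simulated datasets per setting. One further run used AUC 0.85 and prevalence 30%.
- Combinations: five markers with standardised mean shifts 1.4, 0.6, 0.6, 0.5 and 0.7; correlation 0.3; linear discriminant; prevalence 50%; 300 datasets per size.

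**3. Optimism from an in-sample cut-off.** J = sensitivity + specificity − 1. With d = √2·Φ⁻¹(AUC), a marker read at cut-off c has true J(c) = Φ(d − c) + Φ(c) − 1. The cut-off is the one that maximises J in the scored data. Optimism is apparent J minus true J at that cut-off. Examples at AUC 0.80:
- N=300: 0.482 − 0.438 = 0.044
- N=120: 0.501 − 0.431 = 0.070
- N=60: 0.532 − 0.423 = 0.109

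Over all settings:

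| N | Optimism in J |
|---|---|
| 300 | 0.033 to 0.044 |
| 270 | 0.037 to 0.044 |
| 120 (about the CSF subset) | 0.059 to 0.075 |
| 60 (retrospective) | 0.093 to 0.110 |

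At N=300 this is about 1.5 to 2 percentage points each on sensitivity and specificity.

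**4. Optimism from the best combination.** Five markers give 2⁵ − 1 = 31 non-empty subsets. The subset with the highest in-sample AUC is kept:

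| N | Apparent AUC | True AUC | Difference |
|---|---|---|---|
| 300 | 0.853 | 0.841 | 0.012 |
| 125 | 0.861 | 0.834 | 0.027 |
| 60 | 0.875 | 0.821 | 0.054 |

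If the cut-off on that combination is also chosen in-sample, the optimism in J is 0.060, 0.115 and 0.192.

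**5. Device minus benchmark at N=300, equal true accuracy.** The difference in J depends on how the benchmark is read:
- fixed cut-off at its true optimum: +0.026 to +0.032
- fixed cut-off 0.3 SD away from the optimum: +0.045 to +0.049
- cut-off chosen in-sample, as for the device: within 0.002 of zero

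**6. The validation set.** Section 3.2 attaches 300 to Step 2. Section 4.3.3 gives Step 2 as 270, section 4.3.3.2 says 300 covers both steps, and section 4.3.4 counts the first 30 in the baseline set. Table 7 gives 300 to the full study, which is consistent. Only the wording of section 3.2 is out of line.

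**The case against.** The strongest reply is that the Protocol does not say a best cut-off will be selected and reported. Showing performance over a range of cut-offs involves no selection and no optimism; the simulation imposes the selection. Combinations are labelled further analysis, the study is a pilot, and an analysis plan that is not shown may contain the internal validation. This stands in part. It makes the concern conditional and limits its weight. But a primary outcome that compares sensitivity and specificity must be read at some cut-off, and the only rule this document gives is an exploration of several on the device. The combination search is also explicitly for the best.

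A reader might go further in four ways that the documents do not support:

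- **That the comparison is tilted to the device.** The literature cut-offs are stated for forming comparison groups, and the same sentence permits data-driven ones. No cut-off is given for the benchmark in the primary contrast, and the combination search is not limited to the device. The DeLong test treats both platforms alike. Under a common rule the bias is about zero.
- **That the bias is as large as a noninferiority margin.** The Protocol states no margin, so there is nothing to compare it with.
- **That the 30 Step 1 patients train the cut-offs.** They serve to refine the procedure of use. Dropping them leaves the optimism essentially unchanged.
- **That Table 7 should read 270.** It would then be wrong, because it describes the full study.

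**Conclusion.** The point holds in a limited, conditional form. As written, section 4.4.3 lets device cut-offs and marker combinations be explored and scored in the same patients. If the best of them is reported, accuracy is overstated. The amount is modest at N=300 (about 0.03 to 0.04 in J, 0.012 in best-combination AUC). It is larger in the CSF subset (about 0.06 to 0.075, and 0.027) and in the 60 retrospective samples (about 0.09 to 0.11, and 0.054), where these measures are also primary. A device-favouring difference of about 0.03 to 0.05 in J at N=300 is possible but not established, since it arises only if the device alone is tuned. Single-marker AUC comparisons by DeLong are not affected.

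The sizes rest on the assumed AUCs, prevalence, correlations and a J-maximising cut-off, none of which the Protocol gives. The mismatch between sections 3.2 and 4.3.3 on the size of Step 2 is a wording error.

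**What to change.** In section 4.4.3:

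- State one cut-off rule and apply it identically to device and benchmark.
- Report sensitivity, specificity, predictive values and best-combination AUC from repeated cross-validation, with cut-off and combination selection inside each fold, or with a bootstrap optimism correction that repeats the selection in each resample. Do this for both platforms, and also for the CSF subset and the 60 retrospective samples.
- Add a sensitivity analysis that excludes the 30 Step 1 patients, because the procedure was still being refined in them.

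In section 3.2, reword so that 300 is Steps 1 and 2 together and Step 2 is 270. Leave Table 7 as it is.

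Locking cut-offs on the retrospective samples is a possible alternative but a debatable one. They are a selected case-control set that excludes non-AD and mixed dementia, and their results are meant to change the device, so a cut-off fixed there may not carry over to unselected referrals.

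The cost is a little more computing and slightly less favourable figures. In the sensitivity analysis only, confidence intervals would be about 5% wider (√(300/270) = 1.054).

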4.3.5.2. Clinical pilot study sample size considerations

This is a clinical pilot study, i.e., the first study to evaluate and validate AD blood biomarkers measured using the newly developed 2D-BioPAD diagnostic aid in human plasma samples and in clinical environments in three countries. Sample size considerations for the prospective study are summarized in Table 6.

Table 7. Sample size for the prospective study

Study	Sample size	Rationale
Prospective, feasibility	30 patients 3 plasma samples/patient	10 patients per study centre appropriate for an initial feasibility assessment when shifting from a laboratory to a clinical environment. Repeated blood sampling allows initial assessment of use conditions in a clinical environment.
Prospective, full study	300 patients 1 plasma sample/patient	Sample size is in line with recent pilot studies of AD blood biomarkers validating new assessment methods for AD blood biomarkers ²⁵ or studies comparing different assessment methods ^{26,27,28} .
Prospective, feasibility & full study	At least 6 HCPs (2/study centre)	Sample size allows detailed initial feedback from several medical specialties and HCP categories with various degrees of experience.

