4.4.2. Prospective study outcomes

Table 9. Overview of the prospective study outcomes

Outcome type	Description
Primary	
 Sensitivity, specificity, positive and negative predictive values of plasma biomarkers measured with the 2D-BioPAD prototype versus benchmarking equipment (same as above) for identifying AD diagnosis established as per centre-specific standard procedures. Overall experience of HCPs with the 2D-BioPAD diagnostic aid Overall experience of patients with the 2D-BioPAD diagnostic aid
Secondary	
 Comparison of plasma biomarker values between 2D-BioPAD prototype and benchmarking equipment, considering the potential impact of other parameters, e.g., demographics, comorbidities, disease stage Sensitivity, specificity, positive and negative predictive values of plasma biomarkers measured with the 2D-BioPAD prototype for identifying AD-related pathology (e.g., β-amyloid, tau), as indicated by either plasma biomarkers from benchmarking equipment or, where available, CSF biomarkers measured during routine assessments at the clinical study centres using state-of-the-art equipment. Investigating plasma biomarkers measured with 2D-BioPAD prototype versus benchmarking equipment in relation to cognitive, clinical and other data Assess if user experience (HCPs and patients) with the 2D-BioPAD diagnostic aid varies by country, clinical specialty, and/or years of experience Assess if the information provided to HCPs via the digital interface of the 2D-BioPAD diagnostic aid is understandable and relevant Collect feedback for diagnostic aid improvement from HCPs and patients

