Unadjusted 2-sided p-values <0.05 will be considered statistically significant. Adjustment for multiple testing using a false discovery rate (e.g., Benjamini-Hochberg procedure) will be used where relevant.

The main hypothesis is that the accuracy of the 2D-BioPAD system measurements is noninferior to the accuracy of AD plasma biomarkers measured using benchmarking equipment.

Analyses of user experience (HCPs and patients) will include mainly descriptives, with comparisons by country, clinical specialty, and/or years of experience where relevant.

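### Noninferiority is the main hypothesis, but the stated accuracy comparison is a difference test with no margin or confidence-limit rule

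*Protocol*

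**What the plan says.** Section 4.4.3 gives the main hypothesis: "The main hypothesis is that the accuracy of the 2D-BioPAD system measurements is noninferior to the accuracy of AD plasma biomarkers" measured on the benchmarking equipment. The same section supplies the analysis:

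- For predicting diagnosis or CSF status, for each blood biomarker, the "area under the receiver operating characteristic curve (AUC) of the ROCs for 2D-BioPAD and benchmarking measures will be compared with DeLong test".
- The decision rule is general: "Unadjusted 2-sided p-values <0.05 will be considered statistically significant". It is followed by "Adjustment for multiple testing using a false discovery rate (e.g., Benjamini-Hochberg procedure) will be used where relevant".
- For the threshold-based measures: "Sensitivity, specificity, positive and negative predictive values will be assessed for different 2D-BioPAD biomarker cut-offs".

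Table 9 (section 4.4.2) makes primary: "Sensitivity, specificity, positive and negative predictive values of plasma biomarkers measured with the 2D-BioPAD prototype versus benchmarking equipment", for AD diagnosis established by each centre's standard procedures. Accuracy against CSF-defined pathology is secondary.

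Section 4.3.5.2 (Table 7) justifies the 300 patients by precedent: "Sample size is in line with recent pilot studies of AD blood biomarkers validating new assessment methods for AD blood biomarkers". Section 4.1.3 expects CSF results in about 100-150 of the 300.

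**The concern.** A noninferiority hypothesis needs a stated loss of accuracy that would still be acceptable, and a rule that rejects the null of a loss at least that large. Section 4.4.3 has neither. Its DeLong test with p<0.05 addresses a different null, that the two AUCs are equal. A non-significant result may only mean that the sample was too small to show a loss. A significant result may reflect a loss too small to matter. Neither outcome settles the main hypothesis.

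The measures do not line up either. The test is on AUC, while the primary accuracy outcome is sensitivity, specificity and predictive values. For those, the text describes assessment at various 2D-BioPAD cut-offs and no paired comparison with the benchmark. No single marker is named to carry the hypothesis.

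What is at stake is the main statement the pilot will make about the device, which section 5 says will feed into confirmatory, regulatory and market planning.

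**Working it through.** **1. Can the plan's own figure be reproduced?** No. The 300 patients are not derived from a margin, power, expected AUC or prevalence, so the sample size implies no margin.

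**2. Inputs.** From the protocol: N=300 (Table 7), CSF subset 100-150 (section 4.1.3), two-sided 0.05 (section 4.4.3). Assumed, because the protocol does not give them: benchmark AUC 0.90; true loss 0.05; AD share 40% in the simulation and 30-50% in the formula; within-group marker correlation 0.5-0.8 in the simulation; correlation between AUC estimates 0.3-0.7 in the formula; margins 0.05 and 0.10.

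**3. One case by hand (Hanley-McNeil variance).** Take N=300, 150 AD and 150 not, correlation r=0.5 between the AUC estimates.

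Var(A) = [A(1−A) + (n₁−1)(Q₁−A²) + (n₀−1)(Q₂−A²)] / (n₁n₀), with Q₁ = A/(2−A) and Q₂ = 2A²/(1+A).

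- A=0.90: Q₁=0.8182, Q₂=0.8526. Var = (0.09 + 149×0.0082 + 149×0.0426)/22,500, so SE = 0.0185.
- A=0.85: Q₁=0.7391, Q₂=0.7811. Var = (0.1275 + 149×0.0166 + 149×0.0586)/22,500, so SE = 0.0224.
- SE of the difference = √(0.0185² + 0.0224² − 2×0.5×0.0185×0.0224) ≈ 0.0207.
- z = 0.05/0.0207 ≈ 2.41, so P(p≥0.05) ≈ Φ(1.96−2.41) ≈ 0.33.

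In this case the difference test misses a device 0.05 worse in about a third of trials.

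Power of a confidence-limit rule for equal devices at margin 0.05: the SE of the difference is √(2×0.0185²×(1−0.5)) = 0.0185, and Φ(0.05/0.0185 − 1.96) ≈ 0.77.

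**4. Simulated paired DeLong tests (two normally distributed markers, 40% AD, correlation 0.5-0.8).** Share of trials with p≥0.05 when the device is truly 0.05 AUC worse, as ranges over separate runs:

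| N | P(non-significant) |
|---|---|
| 300 | 7-37% |
| 150 | 33-64% |
| 100 | 51-78% |

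The formula, with its wider assumptions, gives 13-61% at N=300 and 42-84% at N=100-150. Both methods show the rate rising as N falls. A valid noninferiority test would hold its false-acceptance rate near 2.5% whatever the sample size.

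**5. The same device under a proper rule.** If noninferiority requires the lower limit of the two-sided 95% CI to lie above −0.05, the device that is 0.05 worse is accepted in about 3-5% of simulated trials (nominal 2.5%).

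**6. Is a proper rule feasible?** Power when the devices are truly equal:

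| Sample | Margin 0.05 | Margin 0.10 |
|---|---|---|
| N=300, formula | 46-94% | 96% to >99% |
| N=300, simulation, 40% AD | about 75-97% | not needed |
| CSF 100-150, formula | 19-69% | 57% to >99% |
| CSF 100-150, simulation, 50% positive | about 34-80% | about 84-99% |

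Whether 300 patients suffice therefore depends on the margin that is missing.

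**The case against.** The strongest defence is that no passage says a non-significant DeLong test will be read as noninferiority. DeLong's method also yields the variance needed for a confidence interval, so a statistical analysis plan could build a valid rule on it. This stands in part. A reader might infer that the protocol prescribes accepting the device on p≥0.05. It does not, and the rates in step 4 are conditional on that reading. But the only rule the protocol does write is the p-value rule, and that rule does not fit the hypothesis. A margin belongs with the hypothesis and the sample size, so this is more than detail left for later.

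A reader might also infer that DeLong is the only comparison of the two devices. It is the only inferential comparison of diagnostic accuracy. Correlation, regression and Bland-Altman analyses are listed too, in an open-ended list. They concern agreement of values and have no acceptance limits, so they do not fill the gap.

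Multiplicity is not ignored: false discovery rate adjustment is provided where relevant. It is simply not tied to the main hypothesis.

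A reader might extend the argument to the 60 retrospective samples. Table 8 lists agreement with the benchmark and the prototype's own accuracy, not accuracy against the benchmark, so the protocol does not tie the noninferiority hypothesis to them.

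Finally, this is a pilot meant to give preliminary information, and the device results do not guide care. That lowers the severity but leaves the mismatch in place.

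**Conclusion.** The point holds as a mismatch between hypothesis and analysis. Section 4.4.3 sets noninferiority as the main hypothesis, gives no margin or confidence-limit rule, and pairs it with a two-sided difference test on AUC. The Table 9 accuracy measures have no paired comparison at all. That much rests on the text alone.

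The size is illustrative. If non-significance were taken as support, a loss of 0.05 AUC would pass in roughly 7-37% of trials at N=300 and 33-78% at N=100-150. The AUC, AD share and correlation behind these figures are assumptions, not protocol values. The documents do not support the stronger claim that the trial will declare noninferiority in this way. Given the pilot purpose this should be fixed, but it does not undermine the study as a whole.

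**What to change.** Amend section 4.4.3 in one of two ways.

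**(a) Keep noninferiority.** Replace the p-value rule for the main hypothesis with: *noninferiority is concluded if the lower limit of the two-sided 95% confidence interval for the paired difference, 2D-BioPAD minus benchmark, lies above minus the margin.* State with it:

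- one named marker;
- one accuracy measure aligned with Table 9, either paired sensitivity and specificity at locked cut-offs, or AUC with Table 9 changed to match;
- the Table 9 reference standard, clinical diagnosis in all patients, with the CSF subset secondary;
- a margin fixed before any Step 2 comparison is seen, with the expected precision at N=300 and at 100-150;
- the Benjamini-Hochberg adjustment already provided for, applied to the remaining markers.

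**(b) Drop the noninferiority wording.** Report paired differences with 95% confidence intervals. This suits a pilot.

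The cost is one paragraph and no new data collection, and an updated protocol is already due by M24. The downside of (a) is that the sample limits the margin. In the CSF subset only a margin of about 0.10 AUC is likely to be supportable. If sensitivity is chosen, only the AD patients contribute, which is 0.40×300 = 120 at an assumed 40%, so the margin must allow for that.
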